### **7.7. Schedule of visits – Phase 1**

Under Phase 1, all enrolled participants will attend routine scheduled visits at the OPCs. Evaluation procedures at each CRICS's visit are indicated in the table and described in details in the sections below. There will be regular contacts by calls by OPC staff if a patient misses scheduled visits as a routine practice.

(Note that under Phase 2, patients screened for CrAg are followed according to the routine OPC procedures, and no additional follow-up visits are conducted or data collected for CRICS apart from whether CrAg-positive patients receive fluconazole.)

### **Visit 0 (V0) – Patients presenting for enrollment in HIV care during implementation period**

## Cryptococcal Retention In Care Study (CRICS)

Patient presenting for enrollment in HIV care at a participating clinic will be briefly informed about cryptococcal disease and CrAg screening on the remnant plasma from their CD4 count sample. (See **7.1. CrAg Screening Implementation (Reflex testing, return of results, communicating results and enrolment into the prospective cohort)**). For patients who have already had a CD4 test done in the 2 weeks before the enrolment date, the remnant plasma from other routine tests ordered on the day of enrollment will be used for CrAg screening. If no other tests are requested on the day of enrollment, the patient will be asked to provide a fresh sample of blood for CrAg screening.

### **Baseline Study Enrollment Visit– All Patients with CD4 $\leq$ 100 cells/ $\mu$ L**

On this visit, the patient will receive their CD4 count and plasma CrAg results. After having the study described to them and the opportunity to ask questions, patients will be asked to sign written, informed consent forms for participation in the study. A urine pregnancy test will be performed for women of childbearing age who are found to be CrAg-positive as described under special populations. A study ID will be assigned to those who have CD4 count  $\leq$  100 cells/ $\mu$ L. A full physical examination will be performed and the Study Enrollment Form will be filled out (Appendix 4: Enrollment). Patients who are CrAg-positive and have no evidence of meningitis will be prescribed and provided with fluconazole treatment for early cryptococcal disease. This will consist of 900mg per day for two weeks. Patients will be supplied with enough fluconazole to last until their next clinical visit (2 weeks). Patients who are CrAg-negative will follow standard clinic care.

Patients who have symptoms suggestive of meningitis or other OI that requires hospitalization will be referred to hospital for evaluation as is routine practice in Vietnam. These patients will remain in the study and hospitalization data will be collected (Appendix 7: Hospitalization)

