## 2. Study Objectives and Outcome Measures

**Table 1. Study objectives and outcome measures**

Primary objectives	Outcome measures
1. To estimate the proportion of people living with HIV (PLHIV) who have advanced disease ( $CD4 \leq 100 \text{ cells}/\mu\text{L}$ ) at presentation to HIV care	
 
Proportion of HIV-infected adults who have <math>CD4 \leq 100 \text{ cells}/\mu\text{L}</math>
 

2. To determine the prevalence of CrAg-positivity among HIV-infected patients with $CD4 \leq 100 \text{ cells}/\mu\text{L}$	
 
Proportion of patients who are CrAg-positive among all HIV-infected adults who have <math>CD4 \leq 100 \text{ cells}/\mu\text{L}</math>
 

3. To determine clinical outcomes including common causes of mortality for PLHIV with $CD4 \leq 100 \text{ cells}/\mu\text{L}$ who are enrolled in a programmatic rollout of screening for CrAg	
 
Reported causes of death
 
Proportion of patients with HIV-related hospitalizations at 6 and 12 months
 
Proportion of patients with new AIDS-defining OIs/conditions at 6 and 12 months
 

4. To estimate the 12-month mortality among two groups of HIV-infected patients with $CD4 \leq 100 \text{ cells}/\mu\text{L}$ who are enrolled in care and treatment: 
 
Those who are CrAg-positive and are treated with high-dose fluconazole;
 
Those who are CrAg-negative.
 
	
 
Twelve (12) month all-causes and CM-related mortality among patients who screen CrAg-positive and CrAg-negative
 

Secondary objectives	Outcome measures

5. To estimate the 12-month retention in care among two groups of HIV-infected patients with <math>CD4 \leq 100</math> cells/<math>\mu</math>L who are newly enrolled in care and treatment:
 
 
• Those who are CrAg-positive and are treated with high-dose fluconazole
 
• Those who are CrAg-negative
 
	
 
• Twelve (12) month retention among patients who screen CrAg-positive and CrAg-negative
 

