### **Enrollment in the follow-up study**

In Phase 1, enrollment in the longitudinal cohort will be offered to eligible patients who have  $CD4 \leq 100$  cells/ $\mu L$  enrolled at and plan to receive ongoing outpatient care at one of the selected study OPCs (Table 2). Those who test plasma CrAg-positive and have no symptoms of meningitis will be treated with high-dose fluconazole. Study participants will be followed from the time of plasma CrAg screening for a minimum of 6 months and up to 12 months depending upon when they are recruited with respect to the study expected duration. Routine clinical data will be abstracted from medical records and supplemental data will be collected to determine treatment outcomes and related factors. Fluconazole will be provided by the study for patients enrolled in the follow-up program during Phase 1 for the duration of the study. For those who tested CrAg-positive and are still receiving maintenance fluconazole at the end of their longitudinal follow up, fluconazole will be provided through routine sources.

In Phase 2, screened patients will not be followed up prospectively. However, fluconazole supply for identified CrAg-positive patients will be provided by the project if patients do not otherwise have access through their OPCs.

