#### **4.2. Exclusion criteria:**

- History of prior CM
- Receipt of systemic antifungal medication for more than 4 consecutive weeks within the past 6 months
- Receipt of ART for more than 4 consecutive weeks within the past year
- For CrAg-positive patients only: Known to be currently pregnant or planning to become pregnant during the study period

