### **Symptomatic patients**

Plasma CrAg-positivity in a person with symptoms consistent with meningitis increases the suspicion for CM. If symptoms of meningitis (e.g., fever, headache, stiff neck) are determined by the treating physician to be present in a CrAg-positive patient, the patient will be referred to the nearest hospital capable of performing an LP and CSF analysis according to national protocols. Data from the hospitalization will be collected for analysis (Appendix 7:

Hospitalization ); however, evaluation and treatment of study participants with symptoms of meningitis will be determined by the treating physician in accordance with national guidelines. Patients with laboratory-confirmed CM will receive induction, consolidation, and maintenance phase therapy as per the Vietnam National HIV Guidelines. These might include intravenous amphotericin B 0.7-1mg/kg/day or high-dose fluconazole for two weeks (induction phase), followed by fluconazole 900 mg/day for 8 weeks (consolidation phase). At the end of the consolidation phase, fluconazole 200mg/day will be prescribed as secondary prophylaxis until  $CD4 >200$  cells/ $\mu l$  for at least 6 months or after viral suppression. This is according to the national protocol and is not considered part of this evaluation [15, 16].

Symptomatic CrAg-positive patients who refuse to have an LP or in whom an LP cannot be done will be offered the same treatment as laboratory-confirmed cases of CM, as outlined in the National Guidelines. If the patient refuses treatment for CM, they will be given oral fluconazole at the same dosage/length as asymptomatic CrAg-positive patients as a final option.

Patients admitted for treatment of CM will remain in the study, and the study point to contact (POC) at the OPC will be responsible for keeping in contact with the hospital to monitor the progress and document the patient's outcome. The OPC staff will abstract information from the inpatient medical record and fill in the study Hospitalization Form (see Appendix)

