## Cryptococcal Retention In Care Study (CRICS)

result). Specifically, for CrAg-positive patients, follow-up forms should be filled out at 2-week after fluconazole, 10-week after fluconazole, 2-, 6-, and 12- month follow-ups after ART initiation. Whereas, for CrAg-negative patients, follow-up forms should only be filled out at 2-6-, and 12- month follow-ups after ART initiation. Follow-up patient variables are listed in the section “up. The history of appointment in all patients and history of fluconazole pre-emptive treatment among CrAg (+) patient will be recorded using Appendix and Appendix 19: Fluconazole preemptive treatment log respectively.

- Patients’ quality of life will be re-evaluated at 6- and 12-month follow-ups after ART initiation.
- If a patient requires hospitalization at any point during their 12-month follow-up period, data about hospitalization will be collected in a ‘Hospitalization Form’ (Appendix 7: Hospitalization **Error! Reference source not found.**). The clinical staff at the study site from which the patient is transferred will take charge of collecting these data after the patient has been discharged or died in the hospital (Appendix 11: Off **Error! Reference source not found.**).
- An ‘Off-Study Form’ (Appendix 11: Off **Error! Reference source not found.**) will be used to collect data related to patient’s status, reason for study termination and to assess endpoints.
- All follow-ups will be performed actively, to minimize patient loss to follow-up. Patients will receive a phone call one day before each scheduled visit to remind them of the appointment. These procedures are intended to minimize loss to follow-up and to ascertain patient status in those with a missed study visit at following enrolment into the screening program.

In this amendment, a number of additional items are added to Enrolment Form, Follow-up Form and Off-study Form (health insurance, date of first registration with the OPCs, number of hospitalizations, and source of causes of death report). Such information will be collected prospectively on those who are enrolled after the approved amendment only.

## Phase 2

**For Phase 2:** patients screened for CrAg will be managed by their providers according to the routine OPC procedures, and no additional study related follow-up visits will be conducted. No

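### Objective 4 asks about CrAg-positive patients treated with high-dose fluconazole, but its outcome measure takes everyone who screens CrAg-positive, including those whose meningitis was already present at baseline

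*Protocol*

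**What the plan says.** - **Population in the objective.** Objective 4 (Protocol Summary and section 2, Table 1) compares CrAg-negative patients with CrAg-positive patients given high-dose fluconazole. The Phase 1 paragraph of the Protocol Summary describes the survival groups in the same way. It sends patients without CNS features to high-dose fluconazole and those with CNS symptoms to care under national guidelines.
- **Outcome measure for that objective.** Table 1: "Twelve (12) month all-causes and CM-related mortality among patients who screen CrAg-positive and CrAg-negative". The treatment condition is gone.
- **Eligibility.** The only CM item in section 4.2 is "History of prior CM". Current CM or current meningitis symptoms are not exclusions.
- **Baseline visit.** Section 7.7: "Patients who have symptoms suggestive of meningitis or other OI that requires hospitalization will be referred to hospital", and then "These patients will remain in the study and hospitalization data will be collected". Section 7.4, Symptomatic patients: "Patients admitted for treatment of CM will remain in the study".
- **Start of follow-up.** Section 3: "Study participants will be followed from the time of plasma CrAg screening for a minimum of 6 months".
- **Analysis.** Section 11 states no split by CNS status at baseline. It plans a proportional hazards comparison of CrAg-positive participants with a historical cohort found CrAg-positive on stored specimens.
- **Objective 3.** Table 1 counts "Proportion of patients with HIV-related hospitalizations at 6 and 12 months". Section 10 collects admission data "If a patient requires hospitalization at any point during their 12-month follow-up period".

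**The concern.** Sections 1.1 and 1.4 give the reason for screening: find cryptococcal disease before meningitis develops, treat it pre-emptively and improve survival. Objective 4 is worded to match. A death from CM already present when the screening result is acted on says nothing about how pre-emptive fluconazole performs. Under the Table 1 measure that death counts together with deaths after pre-emptive treatment.

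At stake is the interpretation of a primary objective. From a single all-CrAg-positive figure, a reader cannot separate late presentation with CM from failure of pre-emptive treatment. The historical-cohort comparison in section 11 has the same problem if the share with CM at entry differs between the cohorts.

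**Working it through.** **1. Do patients with CM at baseline fall inside the measure?** Set the sections side by side.

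- Section 4.2 admits them; sections 7.4 and 7.7 keep them.
- Section 3 starts follow-up at CrAg screening, before the baseline visit, so a later death from that illness is within follow-up.
- The Table 1 measure is defined by screening result alone, so it includes them.

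**2. Does the objective's own wording remove them?** Not cleanly. Section 7.4 lists high-dose fluconazole among the possible induction treatments for laboratory-confirmed CM, so a patient with CM at baseline can be CrAg-positive and on high-dose fluconazole. The same section lets a symptomatic patient who refuses CM treatment receive the asymptomatic patients' regimen. In the other direction, patients who decline fluconazole stay in the study and count in the measure, but not in the objective's group.

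**3. Denominator.** Section 6 reports 25 CrAg-positive among 957 enrolled and projects 1,104 enrolled. 1,104 x 25/957 = 28.8, which reproduces the protocol's figure of about 29. One death is 1/29 = 3.4 percentage points.

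**4. Size of the pooling effect.** Let k of the 29 have CM at the baseline work-up with 12-month mortality d, and let the rest have mortality p. Then

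- pooled mortality = [k d + (29 - k) p] / 29
- shift from p = k (d - p) / 29
- share of deaths from baseline CM = k d / [k d + (29 - k) p]

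The protocol gives none of k, d or p. With d = 30-50% and p = 5-10% as **assumptions**:

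| k | Pooled mortality | Shift | Share of deaths from baseline CM |
|---|---|---|---|
| 1 | 5.9-11.4% | 0.7-1.6 points | 10-26% |
| 3 | 7.6-14.1% | 2.1-4.7 points | 26-54% |
| 6 | 10.2-18.3% | 4.1-9.3 points | 44-72% |

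For k = 3, the smallest shift is 3 x (0.30 - 0.10)/29 = 2.1 points and the largest is 3 x (0.50 - 0.05)/29 = 4.7 points. The shift depends on d - p. Taking p as zero would overstate it.

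**5. Hospitalization, for orientation only.** If a proportion b is admitted from the baseline referral and a proportion h of the others later, the total is b + (1 - b) h. With assumed b = 5% and h = 10-20%, that is 0.05 + 0.95 x 0.10 = 14.5% to 0.05 + 0.95 x 0.20 = 24.0%. This shows what a separate row would reveal. It does not make the total wrong.

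**The case against.** **The objective already names the narrower group.** Read with the Protocol Summary, CM at baseline lies outside the pre-emptive group. This is fair as a reading of intent, but the outcome measure contradicts it and section 7.4 blurs it. What remains is a mismatch between objective and measure, and that mismatch is the point made here.

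**Referral is not disease.** Section 7.7 refers on suggestive symptoms, for evaluation. Section 7.4 provides for patients in whom CM is then excluded and who get the same treatment as asymptomatic patients. This stands: a split by symptoms or referral would misclassify them, so the split must use the result of the work-up.

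**The time origin is not settled.** Sections 7.7 and 10 time the 2-, 6- and 12-month visits from ART initiation. If the 12 months ran from ART, some early deaths could fall outside. But section 3 follows participants from screening, section 10 follows them from enrollment, and Table 1 sets no ART-based origin for mortality.

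**Strata can be left to a statistical analysis plan.** That is true of extra rows, and such a plan may exist. The mismatch between objective and measure, however, is in the protocol.

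**Stronger readings a reader might infer.**

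- *That admissions directed at the baseline visit wrongly inflate objective 3.* The text does not support this. Objective 3 describes everyone enrolled in the rollout, and section 1.4 wants the burden of illness and causes of death in late presenters. Only the opportunistic-infection measure is limited to new events, and that can be deliberate.
- *That the cost per CM death averted is biased.* This is speculative. CM that is symptomatic at presentation arises under the comparator too, and the cost-effectiveness model is not in the protocol.
- *That these patients should leave the cohort.* Keeping them is right for describing the screened population.

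**Conclusion.** The concern holds for objective 4. The objective and its outcome measure name different populations. Followed as written, the measure pools CM present at the baseline work-up with outcomes after pre-emptive fluconazole, so it does not report mortality in the group the objective names. This rests on the protocol's wording and needs no assumed rate.

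The size is unknown. Each death is 3.4 points among about 29 CrAg-positive patients, and the shift is k(d - p)/29. The tabulated values are illustrations. Section 10.2 says that few CrAg-positive patients had developed CM so far, which gives no support to large k, although it does not say how many had CM at baseline.

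For objective 3 there is no error. Showing baseline-referral admissions separately is an optional aid to interpretation.

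**What to change.** 1. In Table 1 and section 11, make the objective 4 population and its measure agree. State whether CrAg-positive patients treated for CM from the outset, and those who decline fluconazole, belong to the named group.
2. Keep mortality in all CrAg-positive patients. Beside it, report all-cause and CM-related mortality by CNS status at the baseline work-up: no CM (including symptomatic patients in whom CM was excluded) versus CM confirmed, or treated as CM, from the baseline referral. List separately any patient whose status was never resolved.
3. Apply the same split descriptively to the historical-cohort comparison where that cohort's data allow it.
4. For objective 3, keep total HIV-related hospitalizations as the burden measure. Optionally add a row for admissions resulting from the baseline referral, identified from Hospitalization Form dates. The baseline variables record only referral for lumbar puncture, so they would miss admissions for other infections.

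The cost is a few lines of text and a few table rows. Baseline symptoms, examination, lumbar-puncture referral and the Hospitalization Form are already collected, and section 10.2 already classifies treated CrAg-positive patients by meningitis and CM diagnosis for costing. Eligibility, procedures and treatment are unchanged. The drawback is that about 29 patients are divided into smaller groups, so the split should be shown as counts with wide intervals and without formal comparison.

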### **Follow-up Visits**

- CrAg-positive patients without symptoms of cryptococcal disease will be seen back at clinic **after two weeks** for evaluation and changing of their fluconazole dose to 450 mg per day (to be taken for 8 weeks) and initiation on ART as per the evaluation guidelines (see Appendix 5: Starting ART Form). They will subsequently return to clinic for an

## Cryptococcal Retention In Care Study (CRICS)

evaluation **eight weeks later**, during which time a dose reduction in their fluconazole to 200 mg per day maintenance dose will be completed.

- Follow-up visits for fluconazole dose changes should occur 2 weeks after fluconazole initiation and then 8 weeks after. If these do not coincide with routine OPC appointment, then non-routine appointments should be made. Patients should be told the importance of coming back to the OPC at those designated times for fluconazole dose changes. CRICS evaluation will be conducted and follow-up data will be collected at these 2 types of follow-up visits.
- CRICS evaluation and follow-up data collection should also be collected at routinely scheduled OPC visits that occur at ART initiation (if not at one of the above follow up visits), 2-, 6- and 12-months after ART initiation. Therefore, all enrolled CrAg-positive patients will be re-evaluated at 2-week and 10-week after fluconazole initiation and 2-, 6-, and 12-month follow-up after ART initiation (referred to as CRICS's visit). The specific date of these CRICS's visits might be decided in consideration of the patients' regularly scheduled clinic visit. In these visits, a short follow-up form (see Appendix 6: Follow-up ) which incorporates information on current symptoms, side effects of fluconazole (if they are on fluconazole) and other clinical outcomes should be filled out.
- CrAg-negative patients will be re-evaluated at routinely scheduled visits for ART initiation and 2-, 6-, and 12-month follow-up visits. The follow-up data collection form should be filled for each of these visits.
- All visits will be documented using Appendix 18: Patient's visit logbook

Cryptococcal Retention In Care Study (CRICS)

**Table 4. Schedule of select procedures and tests**

Procedure	Pre-Study	V0	Baseline visit (Study enrollment)	Follow-up visits
HIV testing	X			
CD4 testing*		X		X (6, 12 months)
Viral load testing*				After 6 and 12 months on ART (If available)
Patient informed about availability of CrAg screening		X a		
Patient provided with CrAg test result			X a	
Written consent			X a	
A urine pregnancy test			X a (for CrAg+ women)	X a (for CrAg+ women whose LNMP is more than 5 weeks prior)
Enrollment Form			X a	
ART initiation form				At the time of ART initiation as recommended by national guideline
Health-related quality of life Form			X a	At baseline, 6- and 12- month follow-ups a
Follow-up Form				For CrAg-positive patients: At 2-week b , 10 week b , 2- a , 6- a and 12 month a follow-ups For CrAg-negative patients: At 2- a , 6- a and 12 month a follow-ups
Starting preemptive therapy of fluconazole-patient with CrAg (+)			X b	

## Cryptococcal Retention In Care Study (CRICS)

Reducing dose of fluconazole			X a (At the first day of 9th week)
Off-study Form			X b (12 months after ART initiation)

aStudy-related procedures, but conducted on patients' routine visits for HIV care.

bStudy-related procedures for CrAg-positive patients that may occur at a time separate from a routine OPC visit.

\*-MOH is in the process of implementing routine viral load monitoring. Results from CD4 and viral load test that are conducted routinely will be collected for CRICS.

### **Minimizing loss to follow-up**

For patients who cannot be reached for a follow-up appointment or miss their follow-up appointment, a study-related red-coloured sticker will be placed on medical records to remind study staff at OPC of scheduled routine clinic visit or study visit. The note will be addressed to the nurse or physician and will be placed in the front of the file reminding them to inform the social worker or other assigned staff who routinely contact patients who miss appointments. We will collect information about routine attempts to contact the patient and immediate outcomes of each attempt will be documented on a study form (see Appendix 8: Late Attendance, Missed Appointment ).

